Mother's in recovery qualitative study. Thirteen mothers currently or recently discharged from substance abuse treatment at Banyan were interviewed regarding family influence on treatment, recovery and relapse, and attitudes/preferences regarding family aftercare. Preliminary review (formal content analysis is ongoing) suggests the following themes: 1) Children and family are the major motivation to remain substance-free; 2) Partner relationships, stress, family problems, shame/guilt, depression and environmental cues are the most challenging for abstinence; 3) Mothers want to involve supportive family members (especially children) in a home-based family aftercare intervention to address family healing, improve communication and support, establish family boundaries, re-establish maternal roles and repair parent-child relationships.

- 4.3. **If you have cited references above, please attach a bibliography, including title, full author list, journal, date and pages. This bibliography should include only those articles referenced above.**

Name	Description	Version
SET R Refs for IRB.docx		0.01

4a. Description of Study (cont'd)

Rationale and Methodology

- 4.4. *** In non-technical, lay language, describe the study design and all study procedures, in order of sequence and timing. Include length of subject participation, what tasks are involved in the study, what tests or procedures subjects will be asked to complete or undergo, specific measures to be used, etc. If applicable, include frequency of visits, duration of visits, and study procedure calendar.**

Study design: The study uses a mixed design in which mothers who are enrolled in outpatient substance abuse/mental health treatment (or treatment for substance abuse as a co-occurring condition) will be randomized to outpatient substance abuse/mental health (or co-occurring) treatment enhanced by Healthy Home (TAU + Healthy Home) or outpatient substance abuse/mental health (or co-occurring) treatment as usual (TAU). Mothers and their minor children enrolled in the study (ages 2-17) will be assessed 4 times at 4 month intervals: Baseline, 4 months, 8 months, and 12 months (with a window for final assessment up to 18 months). Randomization will take place after the baseline assessment.

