- Family Functioning will be measured with the family cohesion subscale of the Family Environment Scale (Moos & Moos, 1981). Family Coping will be measured with two subscales from the Family-Crisis Oriented Evaluation Scales (F-COPES; McCubbin, Larsen, & Olsen, 1996).
- Social Support will be assessed using the Important People Interview (Clifford & Langabuagh, 1991).
- Stigma will be measured using a version of a Stigma scale (Ahern, Stuber, & Galea, 2007).
- Maternal Parenting Functioning will be assessed using the Parenting Practices Questionnaire (Gorman-Smith, Tolan, Zelli, & Huesmann, 1996) and Parenting Self Agency (Dumka, Stoerzinger, Jackson & Roosa; 1996) .

Moderator Measures

- Ethnicity (Black, Hispanic, White non-Hispanic), Socio-economic Status and general demographic information will be collected using demographics items from El Centro and other UM IRB-approved studies.
- Household Composition and Stability will be collected using a Household Composition Form.
- Mother's Stress will be assessed using the Hassles Scale (DeLongis, Folkman, & Lazarus, 1988)
- Mother's Abuse and History of Abuse will be measured using the Violence Scale (Peragallo, 2005).
- Mother's Sleep will be assessed with 4 items regarding sleep from the PROMIS-29 Health Scale.

We will be extracting some information from our intervention clinical forms to capture some of our research constructs. This information includes data related to health assessments, recommendations/referrals, treatment/services rendered, follow-up plan of care, and education. The data collection form has been created in RedCap (Research electronic data capture), an electronic data capture software. A table demonstrating items extracted from the clinical forms is uploaded to the eprost protocol. These clinical forms are kept in the locked research vault at the School of Nursing and Health Studies and will be protected at all times. RedCap data will be kept in password protected files.

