QA monitoring will be conducted by staff of El Centro according to the standard procedures which include a QA review prior to initiation, upon conducting baseline procedures with the

first few study participants, and then for interim reviews.

4.12. * Support the study validity by describing the statistical design, including quantitative and qualitative methods used to analyze data.

The following is the planned data analysis procedure as submitted in the grant application.

-Testing of data quality and distributional assumptions.

Distributions and frequencies of all measures will be examined for non-normality and transformed as needed. If transformation is not sufficient, other distributions (Poisson, Negative Binomial) or nonparametric analyses will be used. Internal consistency will be reported for all measures with Cronbach's alpha. If any scale alphas are below .70, item total correlations and/or factor analysis will be employed to diagnose the psychometric problems and new scales with higher internal consistency will be considered.

-Evaluating the effectiveness of randomization will be accomplished by use of ANOVA and Chi-square of baseline variables. Although not anticipated, if variables with theoretical importance to outcomes show baseline differences by condition, hypotheses tests will statistically control for (baseline) differences.

-Growth curve analysis. Latent growth modeling (LGM) in Mplus 6 (Muthén & Muthén, 2010) will examine change over time in the outcomes. LGM involves creating latent variables representing growth parameters (the baseline or intercept; the linear slope or rate of change, the quadratic slope, etc.). It allows for the simultaneous estimation of multiple growth functions with growth parameters of one function related to growth parameters of another. Mplus allows for outcome variables with distributions that are not continuous (e.g., Poisson for skewed variables or logistic for binary outcomes), which is particularly important with substance use and health outcomes. LGM can generate effect sizes for rate of change or the difference at a single time between the two conditions, i.e., Cohen's d (Cohen, 1992). Following Cohen's (1992) guidelines, we will interpret our effect sizes using the convention of "small" ($d = .2$), "medium" ($d = .5$), and "large" ($d = .8$).

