-Testing hypothesized differences between experimental and control groups will use an intent-to-treat analysis that includes all participants randomized. LGM will examine the effect of treatment condition on trajectories of change separately for each of the outcomes over the one-year follow-up. To test Hypothesis 1, we will assess the trajectories of the mothers' outcomes (mental health, physical health, substance abuse, etc.) and predict of the trajectory of change by intervention condition (Healthy Home vs. TAU). Controlling for the effects of socio-demographic variables and pretest levels of the dependent variables is possible in LGM, if these variables are found to differ by randomization group. To test Hypothesis 2, a similar procedure will consider children's outcomes (mental health, physical health, behavior problems, etc.).

- Testing mechanisms of action. Using Mplus 6, this set of analyses will investigate links between trajectories of change (growth curves) for the hypothesized mechanism of action variables (mediators) and trajectories of mothers' outcomes or children's outcomes following MacKinnon, Lockwood, Hoffman, West and Sheets' (2002) procedures. This method is more powerful than the classic (Baron & Kenny, 1986) method, particularly for binary outcomes. LGM can also test multiple indirect paths or mediators (i.e., Hypothesis 3c) with this method.

- Clinically significant change procedures (Jacobson & Traux, 1991) can also investigate efficacy of an intervention. These procedures: 1) determining whether participants have made statistically reliable change and 2) categorizing subjects according to clinically meaningful cut-points, e.g., recovered (statistically reliable change that moves a client out of clinical range), improved (statistically reliable improvement, but still in the clinical range), and unimproved/deteriorated.

-Implementation analysis will be used to determine the feasibility of adapting Healthy Home for other agencies. Using cost logs for training and service delivery, the total cost of

implementing Healthy Home can be determined. Therapist and agency satisfaction as well as therapist fidelity to Healthy Home will be assessed to determine if changes to the Healthy Home implementation protocol are needed.

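### Covariate adjustment depends on a baseline test between randomized arms, and the plan does not say whether condition may shift the growth-model intercept

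*Combined protocol and SAP*

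**What the plan says.** All the analysis text is in section 4.12.

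- **The test.** The paragraph on the effectiveness of randomization states: "Evaluating the effectiveness of randomization will be accomplished by use of ANOVA and Chi-square of baseline variables". It gives no significance level and no list of variables.
- **The consequence.** The same paragraph continues: "if variables with theoretical importance to outcomes show baseline differences by condition, hypotheses tests will statistically control for (baseline) differences".
- **The same condition, in weaker words.** The paragraph on testing differences between groups is looser about adjustment: "socio-demographic variables and pretest levels of the dependent variables is possible in LGM, if these variables are found to differ by randomization group". One paragraph commits to adjusting once a difference is found; the other only permits it.
- **The growth model.** The growth parameters are listed as "the baseline or intercept; the linear slope or rate of change, the quadratic slope, etc". For Hypothesis 1 the analysis will "predict of the trajectory of change by intervention condition (Healthy Home vs. TAU", and Hypothesis 2 (children) follows a similar procedure. Nothing says whether the intercept is also regressed on condition.
- **Outside the growth model.** The paragraph on distributional assumptions adds: "If transformation is not sufficient, other distributions (Poisson, Negative Binomial) or nonparametric analyses will be used".
- **Timing.** Section 4.4, Study design: "Randomization will take place after the baseline assessment".

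**The concern.** Baseline is measured before allocation, so an arm difference at baseline can only be chance. A test of that difference says nothing about whether adjustment helps. That depends on how strongly the variable predicts follow-up. The plan does limit the rule to variables of theoretical importance, but does not list them, and within that set chance imbalance decides which enter the model. Two analysts could follow the text and fit different models, because the threshold, the candidate set and the force of the rule are all open.

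For the pretest itself the growth model changes the question. The pretest already informs the intercept factor, so what matters is whether condition may shift that intercept. If it may not, the arms share a baseline mean and the pretest is fully used. If it may, the slope effect absorbs chance imbalance and is less precise than it need be. Precision and reproducibility of the model are at stake, not validity of the test on average.

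**Working it through.** **Inputs from the documents.** About 172 mothers (section 4.1), taken as 86 per arm; visits at 0, 4, 8 and 12 months, coded t = 0, 1, 2, 3.

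**Assumed, because the documents give none of them.** 1:1 allocation, two-sided 5%, baseline SD 1, normal outcomes, linear growth, no dropout, a 12-month effect of 0.4 SD (slope effect 0.4/3 = 0.1333), and the covariances below. The plan has no power calculation to reproduce.

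**1. What a baseline test would flag.** At an assumed 5% level the threshold is 1.96 × √(2/86) = 0.299 SD (0.251 SD at 10%). By chance alone 14% of variables would fall between 0.20 and 0.299 SD and go unflagged. With 8 independent variables (number assumed), the chance that at least one is flagged is 1 − 0.95⁸ = 34%.

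**2. Where baseline is not otherwise used (simple month-12 comparison).** Adjustment multiplies the variance by 1 − ρ², with ρ the baseline to follow-up correlation. Simulated at the 5% trigger:

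| ρ | Never adjust | Adjust if flagged | Always adjust | Type I error, adjust if flagged |
|---|---|---|---|---|
| 0.3 | 75% | 75% | 79% | 4.8% |
| 0.5 | 75% | 76% | 86% | 4.3% |
| 0.7 | 75% | 77% | 96% | 3.6% |

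The trigger recovers little of the gain and is slightly conservative.

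**3. Growth model, intercept free by arm versus common.** Let g0 and g1 be the random intercept and slope variances, c their covariance, and σ² the residual variance. The mean of t is 1.5 and its sum of squares is 5. For the between-arm differences, in units of 2/86:

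- intercept variance A = g0 + σ²(1/4 + 1.5²/5) = g0 + 0.70σ²
- slope variance B = g1 + σ²/5
- covariance C = c − (1.5/5)σ² = c − 0.30σ²
- variance ratio, common/free = 1 − C²/(AB)

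*Exchangeable correlation 0.5* (g0 = σ² = 0.5, g1 = c = 0): A = 0.85, B = 0.10, C = −0.15. The ratio is 1 − 0.0225/0.085 = 0.735, a 26% cut. The free SE is √(0.10 × 2/86) = 0.0482 and the common SE is 0.0414. Power is Φ(0.1333/0.0482 − 1.96) = 79% free and 90% common.

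*Slope variance 0.05, c = 0*: A = 0.85, B = 0.15, C = −0.15. The ratio is 1 − 0.0225/0.1275 = 0.824, an 18% cut. Power is 62% free and 70% common.

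*Slope variance 0.10*: the cut is 37%, 13% or 1.5% at c = −0.10, 0 or +0.10. It is zero at c = +0.15, where C = 0 (intercept-slope correlation 0.15/√(0.5 × 0.10) = 0.67).

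*Serial correlation 0.6 or 0.7* (generalized least squares): cut 41% or 33%.

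**4. The trigger inside a free-intercept growth model.** If flagging leads to a common intercept (one way to implement the rule; the plan names none), power at exchangeable 0.5 is 79% free, 80% with the 5% trigger and 90% common. Across the cases simulated, type I error of the trigger rule is 3.9% to 5.0%. The mean free-intercept estimate is 0.400 for a true 0.4.

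**5. Effect of an unflagged imbalance.** At exchangeable 0.5 the free-intercept slope has covariance −0.15 with the baseline difference (unit variance). A 0.2 SD imbalance therefore shifts the 12-month effect by 3 × (−0.15) × 0.2 = −0.09 SD. Across other covariances tried it ran from −0.16 to −0.03, and the sign can reverse at a high intercept-slope correlation (+0.03 at slope variance 0.10 and correlation 0.9). With a common intercept the shift is zero.

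**The case against.** The strongest reply is that the growth-model loss may not exist. Section 4.12 separates the baseline or intercept from the rate of change, then has condition predict the trajectory of change. In that vocabulary the likelier meaning is slope only, which is a common intercept. This stands: on that reading the results in steps 3 to 5 do not arise, and there is nothing to gain on the pretest. What does not go away is that the path is never stated, and that pretest control is offered as a conditional extra, which a common intercept would make unnecessary.

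Second, the rule already filters on theoretical importance, so it is not blind to prognosis. That is fair. But the filter has no list, and inside it the data-driven test still decides. No loss of precision is computed here for omitted socio-demographic variables, because the documents give nothing on how well they predict outcome.

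Third, the nonparametric route is remote: it arises only if transformation fails, and non-normal outcomes can also be fitted within the growth model. The month-12 comparison in step 2 is an illustration, not an analysis the plan names. The 5% trigger level is likewise an assumption.

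A reader might infer that testing baseline first and then choosing the model inflates type I error or biases the result. Neither follows. Allocation is random, the estimates are unbiased over randomizations, and the trigger rule is at or slightly below 5% in every case computed.

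**Conclusion.** The point holds as a defect of specification with a cost in precision. The plan's stated rule selects covariates by chance imbalance within an unlisted set, at an unstated threshold, and with two different degrees of obligation. Where baseline is not already in the analysis, most of the available gain is lost: 76% against 86% power in the month-12 illustration at correlation 0.5.

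For the growth models the size depends on the unstated path. It is zero on the pretest if condition predicts slope only. If the intercept is free by arm, the variance cut forgone is about 0% to 41%, for example 79% to 90% power at exchangeable correlation 0.5, or 62% to 70% with slope variance 0.05 and zero covariance. These are examples, not bounds: every covariance, the effect size and the significance level are assumed, and dropout and clustering of siblings are left out of these figures. It would go too far to say that the trial has lost this power, since the documents never commit to a free intercept.

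The change is worth making at medium confidence, because it costs almost nothing and the common intercept was never less precise in the cases computed.

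**What to change.** In section 4.12:

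1. Delete the ANOVA and chi-square trigger. Report baseline characteristics by arm descriptively.
2. State that, with time coded zero at baseline, the path from condition to the intercept is fixed at zero in every mother and child growth model, whatever the baseline comparison shows.
3. In any analysis outside a growth model, always adjust for the baseline value of the outcome where the method allows. For a rank-based comparison this can be rank analysis of covariance on the baseline rank.
4. Replace the socio-demographic trigger with a short covariate list chosen for expected prediction of the outcome. Candidates are already collected (section 4.4, Moderator Measures: "Ethnicity (Black, Hispanic, White non-Hispanic), Socio-economic Status and general demographic information will be collected using demographics items"), but the plan lists them as moderators and does not show that they are prognostic, so the choice needs a reason. Fix the list before outcomes are compared by arm. Requiring it before any outcome is collected may no longer be feasible, because section 4.4 (child medical condition measure) provides for participants who have already finished all assessments.
5. With the trigger gone, remove both conditional sentences, which also ends the conflict between required and optional control.

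The cost is plan wording and slightly more analysis work. No new data are needed.

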Nurse Progress Notes. These measures take information from clinical progress notes completed by nurses in the Healthy Home condition. There are 2 parts of this measure. First, the nursing intake note will be transcribed into an electronic format. Second, clinical progress notes for each nurse visit will also be transcribed into an electronic format. The transcription is similar to a chart review process, and will be completed for each family member's health status using clinical forms based on the standard documents used as clinical progress notes by Banyan.

We are requesting a waiver of consent for this data extraction. All subjects involved sign consent for the parent study. This data will be analyzed using secondary analysis.

Follow-up for positive clinical indicators. Mothers or children who report suicidal thoughts or intention to hurt others will be interviewed by a licensed health professional on site or by

telephone, or staff will call the Crisis Stabilization Unit or 911 as indicated. Reports of child abuse or neglect will be reported to the authorities as per Florida law and to corresponding SET or TAU clinical supervisor for follow-up.

Contacts with mother/family participants will be conducted in the candidate/participants' preferred language (English or Spanish). Data will typically be obtained in interviewer format as follows. The data collector will meet with the participant in a private room, read the questions and the participant will have the items and responses to read along. The assessor will enter the participant's responses on a computer. Children will complete questionnaires appropriate to their age. Younger children will have the clinical measures only. Data will typically be collected at the sites where the mothers receive substance abuse treatment. Home-based assessments will be offered. It is estimated that data collection procedures will take 90 minutes for mothers (+30 minutes x number of children) and 50 minutes for children. Breaks will be offered and snacks may be offered.

Interventions. The study intervention period is scheduled for 4 months. Healthy Home and substance abuse treatment services received by mothers in both conditions will be tracked to compare intervention exposure across conditions. Mothers in both conditions will be free to access any health or substance abuse services offered in their communities.

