4.4.A. Standard Measures: Click the "Add" button to open the search window, then click the "Find" button to browse and select measures.

Name of Measure	Brief Description	Type of Measure
There are no items to display		

NOTE: A copy of the first page of each standard measure is provided in the [Library of Standard Measures](#) for verification. Ensure that the version being used in this study is the same as the version that has been selected.

Upload any questionnaires and/or assessment tools to be used that are not listed above:

Name	Description Version
Child Behavior Checklist Preschool CBCP.040813.docx	0.01
Child Behavior Checklist Schoolage CBCS.040813.docx	0.01
CHILD DEMOGRAPHIC INTAKE FORM CDIM.docx	0.03
Child Health Questionnaire Physical and Fam Scales Child Report CHQC.041013.docx	0.01
Child Health Questionnaire Physical CG and Family Scales Mother Report CHQM. 041013.docx	0.01
Child's BMI BMIC.040913.docx	0.01
Family Environment Scale Cohesion FES.040913.docx	0.01
FCO FCOPES bilingual.docx	0.01
FI Dental Care Study Child Rating FDSC.040813.docx	0.01
FL Dental Care Study Mother Rating Child FDSM.040813.docx	0.01
FL Dental Care Study Mother rating herself FDSW.040813.docx	0.01
Healthy Home Hassles Scale (HHH).docx	0.01
Healthy Home Important People Interview (IPI) English.docx	0.01
Healthy Home Important People Interview (IPI) Spanish.docx	0.01
HLF Health Literacy Screener HLF.041513.docx	0.01
Household Composition Form HCF.040913.docx	0.01

MDIF Mother Demographic-Translation v2.doc	0.05
Measures_Table_for IRB protocol.04-16-2013.docx	0.01
Modified Stigma Scale with Alcohol MSS.040913.docx	0.02
MSF (Mother Screening Form) with mental health.010914.	0.01
Oral Health Impact Scale Mother rating self OHIP.040913.docx	0.01
Pap Smear Last Check Form LCF.040913.docx	0.01
Parenting Practices Child Report PPC.041013.docx	0.01
Parenting Practices Parent Report PPP.040813.docx	0.01
Parenting Self Agency PSA.040813.docx	0.01
PER--Parent Relationship With Peer Group-Parent (English).doc	0.01
PER--Parent Relationship With Peer Group-Parent (Espanol) (DD).doc	0.01
PROMIS SF v1.0 - ED-Anxiety-SF8a Spanish.pdf	0.01
PROMIS SF v1.0 - ED-Anxiety-SF8a.pdf	0.01
PROMIS SF v1.0 - ED-Depression-SF8a Spanish.pdf	0.01
PROMIS SF v1.0 - ED-Depression-SF8a.pdf	0.01
SET-R Addiction Severity Index LITE (ASI).RX accomodation.docx	0.01
SET-R Form 90 (F90).doc	0.01
SET-R PROMIS 29 Profile ENGLISH.docx	0.01
SET-R PROMIS 29 Profile SPANISH.docx	0.01

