To be eligible for the study Mothers must meet all of the following criteria: (1) Enrolled in outpatient substance abuse or mental health treatment (or treatment for substance abuse as a co-occurring disorder) or case management for mental health or substance abuse problems, (2) have at least one child age 0-17 with whom she has at least monthly contact (3) be age 18 or above, (4) capable of giving informed consent and comprehending either English or Spanish, (5) willing and able to participate fully in the protocol (e.g., to accept assignment to either condition, to provide sufficient locator information for follow-up, to allow their treatment sessions to be monitored for fidelity/process assessment and supervision).

To be eligible for the study Children must meet all of the following criteria: (1) biological, step or adopted child of a mother enrolled in the study and with whom the mother has at least monthly contact (2) age 2-17, (3) has the signed permission of a legal guardian to enroll in the study, (4) gives assent to participate in the study if age 7 or above.

5.8. * Will only one group of individuals be systematically selected and recruited for this study (e.g., welfare patients, racial and/or ethnic minorities, persons confined to institutions or persons determined to be incapacitated)?

Yes No

5.8.A. If yes, please state how this participant group will benefit from the results of the research and provide the reasons and justifications to target this group:

This study focuses on women in substance abuse/mental health treatment and their children. These groups are at high risk for significant health consequences and there is a need for culturally-informed interventions tailored to address their unique needs.

5c. Research Involving Pregnant Women or Fetuses

Pregnant woman or fetuses may be involved in research if **ALL** of the following conditions are met (all items must be justified):

(a) **Where scientifically appropriate, preclinical studies, including studies on pregnant animals, and clinical studies, including studies on nonpregnant women, have been conducted and provide data for assessing potential risks to pregnant women and fetuses.**

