Mothers will be recruited from substance abuse/mental health treatment sites run by Banyan. Study staff employed by Banyan will invite all women who are enrolled in outpatient substance abuse, mental health (or co-occurring) treatment and who have children ages 0-17 to participate in the study. Study staff will contact candidates up to 4 times to offer study enrollment. Candidates who express interest in participating will be administered a screening interview by phone or in person. Study staff will explain the study and if the mother agrees to participate she will be read and asked to provide signed consent and permission for her children to participate.

In addition, study personnel will reach out to personnel from sites that refer women to Banyan for outpatient substance abuse or mental health treatment. This includes Banyan-affiliated residential substance abuse treatment sites, Family Intervention Services, the drug courts and other venues. The study team members will talk to personnel of those sites about the study and

provide them with IRB-approved study flyers and pamphlets and ask them to distribute these materials to mothers who might be referred to Banyan for outpatient substance abuse treatment. Study staff will ask local agencies that serve women who receive mental health or substance abuse treatment to provide contact information for their clients who have consented to be called regarding the study. Those women will be called by study staff for recruitment to the study. We will also use social media (e.g., Craigslist) to broadcast information about the study as a means of promoting recruitment. Potential participants will have to call the study number - there will be no direct communication with individual study candidates via social media.

In addition, the study will accept self-referrals from women who are receiving substance abuse, mental health (or co-occurring) treatment at other centers (besides Banyan). Study staff will inform staff at substance abuse/mental health treatment center about the study and will provide them with flyers and pamphlets. Staff from the substance abuse/mental health treatment center will post/distribute flyers/pamphlets and those clients who are interested will contact the study.

After obtaining the mother's informed consent to enroll in the study, study staff will administer the Child ID Form to identify children who are eligible to participate.

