NOTE: "Alteration of consent" is when the consent procedure does not include, or alters, some of the required elements of informed consent. This only applies to studies conducted by state or local government on public benefit or service programs. See <http://www.hhs.gov/ohrp/humansubjects/assurance/consentcls.htm>

7.2. * **Is a waiver of informed consent being requested?**

Yes No

NOTE: This indicates there is no consent process; waiver criteria need to be justified.

7.3. * **Is a waiver of signed consent being requested?**

Yes No

NOTE: This indicates that the consent process will occur, but there is no signed consent (i.e., verbal script or consent letter).

7b. Informed Consent (cont'd)

7.8. * **Under which of the following criteria does this research qualify for Waiver of Signed Consent?**

Check one	Description
 45 CFR 46.117 (c) (1)	The only records linking the subject and the research would be the consent document, and the principal risk would be the potential harm resulting from a breach of confidentiality. Each subject will be asked whether the subject wants documentation linking the subject with the research, and the subject's wishes will govern.
 45 CFR 46.117 (c) (2)	This research presents no more than minimal risk of harm to subjects and involves no procedures for which written consent is normally required outside of the research context.

7.8.A. * **Please state the justification for the criterion selected above:**

We are requesting a waiver of signed consent for screening. The questions asked for the mother's screening are innocuous - e.g., her age, whether she has minor children, whether she has monthly contact with any of those children.

7c. Informed Consent (cont'd)

7.9. * **Describe the specific steps for obtaining informed consent (e.g., by whom, his/her credentials, language, where, when, etc.):**

Not applicable

CITI certified study staff will explain the study to the mother and if she agrees to participate she will be asked to provide signed consent and permission for her eligible children to participate.

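### Section 4.12 gives no method for sibling correlation in the child outcomes, although mothers are randomised and several children per mother can enrol

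*Combined protocol and SAP*

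**What the plan says.** Section 4.4 makes the mother the unit of randomisation: "mothers who are enrolled in outpatient substance abuse/mental health treatment (or treatment for substance abuse as a co-occurring condition) will be randomized".

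Several children per mother can enter the study:
- Section 5.7 admits any "biological, step or adopted child of a mother enrolled in the study", subject to age 2-17, monthly contact, permission and assent. It sets no limit of one per mother.
- Section 6.2: after the mother consents, "study staff will administer the Child ID Form to identify children who are eligible to participate".
- Section 7.9: "she will be asked to provide signed consent and permission for her eligible children to participate".
- Section 4.4 budgets assessment time as "90 minutes for mothers (+30 minutes x number of children) and 50 minutes for children".
- Section 6.5.A pays the mother a bonus that depends on every one of her enrolled children attending.

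Section 4.12 describes a latent growth model in Mplus for the mothers, with treatment condition predicting the trajectory of each outcome. For the children it adds only "To test Hypothesis 2, a similar procedure will consider" their outcomes. Nothing in 4.12 mentions siblings, nesting, a two-level model, cluster-robust standard errors, an intraclass correlation or the choice of one index child.

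The number of siblings contributing will differ by outcome. Section 4.4 says "Younger children will have the clinical measures only", and the uploads in 4.4.A include a separate preschool form ("Child Behavior Checklist Preschool CBCP.040813.docx") beside the school-age one.

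**The concern.** Treatment is assigned to the mother, so all her enrolled children are in the same arm. Siblings who share a household, a mother and, in the intervention arm, the same nurse visits may well change together. If so, a second sibling adds less information about the treatment effect than an unrelated child would. A growth model with the child as the only unit gives each sibling full weight as an independent observation. The standard error of the treatment effect on slope is then too small, the confidence interval too narrow, and the test rejects a true null too often.

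Child outcomes are Specific Aim 2, so this is not a side analysis. The mediation models for child outcomes share the gap, as do the moderator models. Leaving the method unstated also means it could be chosen after the results are known.

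**Working it through.** The plan gives no power calculation, significance level or intraclass correlation, so there is no figure of its own to reproduce. The check asks what a single-level child model would do.

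**Inputs from the documents**
- About 172 mothers (4.1); four assessments at 0, 4, 8 and 12 months (4.4).
- Children per mother in the earlier trial's subgroup (4.2): m = 42/25 = 1.68.
- Outer scenario (5.2.B): (800 − 172)/172 = 628/172 = 3.65, if every subject who is not an enrolled mother is a child.

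**Assumptions, not in the documents**
- True sibling slope correlation (ICC) 0.1, 0.3 or 0.5; slope reliability R 0.4 or 0.7. The correlation between estimated slopes is then ICC × R, from 0.04 to 0.35.
- Two-sided 5% test, 1:1 allocation, complete data, no treatment effect, family size 1 + Poisson(m − 1).

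**Formula.** Let q be the share of children measured on the outcome.

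DEFF = 1 + q × [(m − 1) + (m − 1)/m] × ICC × R

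The correct standard error is √DEFF times the single-level one. The actual rejection rate is 2 × [1 − Φ(1.96/√DEFF)].

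**m = 1.68, all children measured.** The bracket is 0.68 + 0.68/1.68 = 1.085.

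| ICC | R | DEFF | SE ratio | Rejection, formula | Rejection, simulated |
|---|---|---|---|---|---|
| 0.1 | 0.4 | 1.043 | 1.021 | 5.5% | 5.3% |
| 0.3 | 0.4 | 1.130 | 1.063 | 6.5% | 6.5% |
| 0.5 | 0.4 | 1.217 | 1.103 | 7.6% | 8.0% |
| 0.1 | 0.7 | 1.076 | 1.037 | 5.9% | 6.0% |
| 0.3 | 0.7 | 1.228 | 1.108 | 7.7% | 8.1% |
| 0.5 | 0.7 | 1.380 | 1.175 | 9.5% | 9.8% |

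Each simulated setting used 20,000 replicates. Clustering on mother gave 5.2-5.6%.

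**Half the children measured (q = 0.5, assumed, siblings measured independently).** About 172 × 1.68 × 0.5 = 144 children contribute, from 172 × (1 − 0.5e^(−0.34)) = 111 mothers. Rejection is 5.2-7.2% by formula and 5.3-7.5% simulated.

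**Treatment by a binary mother-level moderator, m = 1.68.** Simulated rejection is 5.4-9.6%; with clustering on mother, 5.1-5.6%.

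**Outer scenario, m = 3.65.** The bracket is 2.65 + 2.65/3.65 = 3.376. DEFF runs from 1.135 to 2.182 and rejection from 6.6% to 18.5% (simulated 6.6-18.7%; clustered 5.2-5.4%).

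**Separate simulation with other inputs.** This used slope variance 0.1, residual variance 0.5 and 4,000 replicates. With four unit-spaced waves, R = 0.1/(0.1 + 0.5/5) = 0.5.
- At a mean of 1.68 children, slope ICC 0, 0.1, 0.3 and 0.5 gave 5.1%, 5.5%, 7.1% and 8.1%.
- At a mean of 3.6 they gave 4.6%, 7.1%, 11.2% and 15.6%.
- With slope ICC 0 but sibling errors at each wave correlated 0.3, as could happen when one mother rates all her children, rejection was 7.3% and 10.8%.
- Clustering on mother held 4.6-5.8% throughout.

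**Does each remedy work? (m = 1.68)**
- A mother-level random intercept alone gives 5.5-9.5% in large samples, the same as ignoring clustering, when the child-level intercept and slope covariance is unconstrained. In 730 simulated four-wave fits the slope standard error did not change.
- Mother-level random intercept and slope gives 5.0% in large samples. In four-wave maximum-likelihood fits at ICC 0.5 and R 0.7 (6,597 replicates, all converged) it gave 5.3%, against 9.1% ignoring clustering and 5.0% clustered. A run with a looser optimiser gave 5.1-6.9% (2,000 replicates), so convergence needs checking.

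Mediation models were not computed.

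**The case against.** The strongest reply is that this is silence, not a stated error. Section 4.12 reproduces a grant text inside an ethics form. A similar procedure need not be an identical one, and Mplus could fit a clustered model. That is fair, and it is why the conclusion is conditional. But what the software can do is not what the plan specifies. The reference in 4.4 to a mixed design introduces the arms and assessments, not a family-level model.

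The size rests largely on assumptions. The 5% level, the 1:1 allocation and complete data are not in the documents, and 4.12 itself expects loss to follow-up. The 1.68 comes from 25 HIV-positive women in another trial and is not a forecast for this one. The 3.65 treats a total not broken down by role as mothers and children only, although it may include other adults at family visits or pilot families. All this stands: the figures are illustrative, and the 3.65 scenario should not drive the severity. With no primary child outcome or threshold named, interval width is the clearer harm. For the moderator analyses, which the plan calls exploratory, it is the only one that matters.

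Two modelling points also stand. Shared rater error inflates rejection even when true slopes are uncorrelated, so 5.5-9.5% is not an upper bound. The smaller effect for partly measured outcomes assumes siblings are measured independently. Measurement depends on age, and if siblings were measured all or none, the design effect would not fall at all.

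**Conclusion.** The concern holds. The mother is randomised, several of her children can enrol, and section 4.12 does not say how their correlation enters the Aim 2 models. If the single-level model is used and sibling slopes are positively correlated, the standard errors are too small.

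Confidence is high for the omission and the direction of the error, and much lower for any one magnitude. At the only family size the documents report, the inflation is modest. It grows with family size and is usually smaller for outcomes measured in only some siblings. A correction before analysis is warranted; the design itself need not change.

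**What to change.** Add to section 4.12 that all child outcome, mediation and moderation models treat children as nested within mother, and name the method:
- standard errors clustered on mother; or
- a two-level growth model with both a mother-level random intercept and a mother-level random slope.

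The text should say that a mother-level random intercept alone is not enough, because it leaves the slope test uncorrected. Report the number of mothers and of children contributing to each child outcome. One index child per mother, chosen by a prespecified rule, would also remove the problem but would discard sibling data.

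The cost is one sentence, and no new data are needed. Clustering on mother is a single model setting. The two-level model takes more work for the Poisson or logistic outcomes that 4.12 foresees. Child confidence intervals become about 2-17% wider at 1.68 children per mother under the assumed range.
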